## 1.2 Trial design

This is an investigator-initiated, human clinical trial designed to evaluate the safety and functionality of the FAST PV and mGFR Technology in CHF patients.

Patients enrolled in the study will be administered VFI (Day 1) and with a second dose occurring 48h (+/- 5h) after the initial dose (Day 3).

After consenting to be enrolled in the study, patients meeting the enrollment criteria will receive a single dose of VFI. Blood draws (approximately 2 mL) will be collected pre-dose and at

---

15 ( $\pm 5$ ), 30 ( $\pm 5$ ), 60 (+30), and 180 (+120) minutes post-dose. The physician will remain present at the bedside of the patient for 10 minutes after administering the FAST VFI. Thereafter, the patient will be monitored on an ongoing basis, with clinical staff assessing the patient's condition along with the 15, 30, and 60 minutes blood draws specified in the protocol.

Patients will be treated according to standard of care throughout the time of their hospitalization. A second dose of VFI will be administered 48h (+/- 5h) after the initial dosing. Blood draws (approximately 2 mL) will be collected pre-dose and at 15 ( $\pm 5$ ), 30 ( $\pm 5$ ), 60 (+30), and 180 (+120) minutes post-dose.

Prior to administering the first and second dose of VFI, the physician will be asked to complete a very brief survey to provide a qualitative assessment of the patient's perceived volume status and renal function prior to initiating the FAST PV and mGFR measurements.

Laboratory values and assessments (see Table 1) will be captured on each day that the VFI is administered and these data will be entered into the case report form. Any AEs determined by the investigator will be captured. Patients will also receive a follow up phone call 7 days ( $\pm 2$  days) after the first dose of VFI was administered, and a second follow up call 30 days after the first dose of VFI was administered as an end-of-study follow up call. Any AEs determined by the investigator will be captured during the follow up calls and will be followed to resolution. Additionally, in-person follow-up visits may be scheduled as needed.

Table 1: Schedule of Study Events/Examinations

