### 4.3 Secondary variables

#### 4.3.1 Efficacy

- Estimated PV (by Kaplan-Hakim's formula, see chapter 7.2) and measured PV (assessed by FAST methodology) on days 1 and 3
- Estimated TBV (by Nadler's formula, see chapter 7.2) and measured TBV (mTBV: calculated from mPV and measured hematocrit, see chapter 7.2) on days 1 and 3
- Estimated GFR (CKD-EPI formula, sMDRD, Cystatin C formula, and Creatinine-Cystatin C formula, see chapter 7.2) and measured GFR (assessed by FAST methodology) on days 1 and 3 in heart failure patients undergoing active fluid management
- Development of AKI within 72 hours after day 1 and 48 hours after day 3 respectively
- Current level and level within last 24 hours of well-being, dyspnea, dizziness, nausea reported on day 1 and day 3
- Subjectively reported symptoms (PGA, dyspnea, dizziness, nausea) determined using patient symptom assessment sheets within the following 24 and 48 hours on day 1 and following 24 and 48 hours on day 3
- Low-output complications within the next 24 and 48 hours (e. g. subjectively reported dizziness/nausea, PGA, hypotension (Systolic <100, diastolic <60mmHg), need for iv-fluid therapy) at day 1 and within the next 24 and 48 hours at day 3
- Risk of being refractory to diuretic therapy (e. g. require dosage increases of furosemide/torsemide, require ultrafiltration/RRT within the next 24-48 hours, fail to improve subjectively in PGA and dyspnea scales) within 24 and 48 hours on day 1 and day 3

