To evaluate whether patients with a high mPVS ( $> +10\%$ ) or a high mTBVS ( $> +10\%$ ) on day 1 and/or day 3 are at risk of being refractory to diuretic therapy (defined as any dosage increases of furosemide i.v. dose equivalent, adding thiazide after day 1, require ultrafiltration/RRT within the next 24-48 hours, fail to improve subjectively in PGA and dyspnea scales, fail of mean weight loss during the study period Day 1-Day 5 of at least 0,5 kg/d) logistic regression models using mPV and mTBV as independent variables will be used.

To evaluate whether the changes of ePV (using relative and absolute change as well as the Strauss' formula) and eTBV (using relative and absolute change) from day 1 to day 3 adequately reflects the changes of mPV and mTBV Bland-Altman plots will be generated. These plots will be analysed exploratory, since no appropriate values for limits of agreements are available. The amount of values within 10% and within 30% of the measured values will also be determined. In addition, the diagnostic test accuracy including 95% confidence interval as proposed by Obuchowski will be calculated.

To evaluate whether the change of mPV and mTBV and changes of mPVS and mTBVS from day 1 to day 3 as well as the mPVS and mTBVS on Day 1 and Day 3 is predictive of the remaining length of stay at the given day (i.e. remaining length of stay starting with day 1 or with day 3), dialysis/ultrafiltration requirement, or rehospitalization within 30 days, or mortality, linear (remaining length of stay), logistic (dialysis/ultrafiltration, rehospitalization within 30 days) or Cox-regression models (mortality) will be utilized using changes of mPV and mTBV from day 1 to day 3 (first model), changes of mPVS and mTBVS from day 1 to day 3 (second model), and mPVS and mTBVS at day 1 (third model) and day 3 (fourth model) as independent variables.

To evaluate whether the percentage changes of mGFR from day 1 to day 3 ( $< 0$  vs.  $\geq 0$ ; continuous) predicts the percentage changes of eGFR from day 2 to day 4 (CKD-EPI formula only;  $< 0$  vs.  $\geq 0$ ; continuous), a logistic as well as a linear regression model will be used.

The same will be done to investigate the changes in eGFR from day 1 to day 3 (all formulas) as the dependent variable. Further, exploratory Bland-Altman plots without predefined limits of agreement will be created.

To evaluate whether patients with a high PVS or TBVS on Day 1 ( $> +10\%$ ) and a decreasing PVS

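### SAP 7.7.1 anchors weight loss and added thiazide to Day 1 in the refractory-to-diuretics outcome, so the Day 3 model scores events that precede its predictor, contrary to the windows in SAP 4.3.1

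*SAP*

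**What the plan says.** SAP 7.7.1 (Efficacy) plans to evaluate whether patients with high volume status "on day 1 and/or day 3 are at risk of being refractory to diuretic therapy". It gives one definition of refractory for both index days:

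- **Diuretics and renal replacement:** "any dosage increases of furosemide i.v. dose equivalent, adding thiazide after day 1, require ultrafiltration/RRT within the next 24-48 hours".
- **Symptoms:** no subjective improvement in PGA and dyspnea, with no reference day given.
- **Weight:** "fail of mean weight loss during the study period Day 1-Day 5 of at least 0,5 kg/d".

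The stated analysis is "logistic regression models using mPV and mTBV as independent variables will be used".

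SAP 4.3.1 lists the same outcome with a closing window that covers the whole list: "within 24 and 48 hours on day 1 and day 3". That list names dose increases, ultrafiltration/RRT and symptom failure. It names neither thiazide nor weight loss, and SAP section 8 (Changes from the protocol) does not record their addition.

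On timing, SAP 1.2 states: "A second dose of VFI will be administered 48h (+/- 5h) after the initial dosing".

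**The concern.** A model that uses the Day 3 volume as predictor should have an outcome that starts at or after the Day 3 measurement. Two components of the 7.7.1 definition are tied to Day 1 whichever day supplies the predictor: weight loss and "adding thiazide after day 1". Dose increases and symptom failure carry no start day there.

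Diuresis between Day 1 and Day 3 can affect the Day 3 volume and is also part of the outcome. An association can then appear even if the Day 3 volume says nothing about what follows. The SAP's general remarks say the analyses are meant to generate hypotheses for phase III, so a Day 3 risk signal built partly from earlier events would be a poor basis for that step.

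The SAP handles the neighbouring outcomes differently. AKI is counted within 72 hours of Day 1 and 48 hours of Day 3, low-output complications over the following 24 to 48 hours, and length of stay as the time remaining from the given day. Forward windows are its own standard, and this outcome departs from it.

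**Working it through.** The plan states no sample size, power or alpha for this analysis, so there is no figure to reproduce. The check is on windows and arithmetic.

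**1. Share of the weight window before the Day 3 measurement.** Inputs: second dose at 48 h ± 5 h (SAP 1.2); Day 1 to Day 5 taken as 4 × 24 = 96 h.
- 43/96 = 45%; 48/96 = 50%; 53/96 = 55%.

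**2. Threshold.** At 0.5 kg/d, Day 1-5 requires 0.5 × 4 = 2.0 kg (2.5 kg if read as five days). The same rate over Day 3-5 requires 0.5 × 2 = 1.0 kg.

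**3. Two patients scored on the weight component.**

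| Loss Day 1-3 | Loss Day 3-5 | Mean Day 1-5 | SAP score | Mean Day 3-5 | Score after Day 3 |
|---|---|---|---|---|---|
| 3.0 kg | 0 kg | 3.0/4 = 0.75 kg/d | not refractory | 0 kg/d | refractory |
| 0 kg | 1.6 kg | 1.6/4 = 0.40 kg/d | refractory | 1.6/2 = 0.80 kg/d | not refractory |

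Dividing by five days (0.60 and 0.32 kg/d) leaves both SAP scores unchanged.

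**4. Thiazide.** Read literally, a thiazide added on Day 2 with no change after Day 3 is an event in the Day 3 model.

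**5. Can this create an association?** Illustration on assumptions that are not in the documents: 3,000 simulated trials of 50 patients; weight loss with mean 1 kg and SD 1 kg in each two-day half; loss after Day 3 unrelated to Day 3 volume; weight component only; univariable logistic regression. The two weight rules disagree in about 25% of patients.

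| Assumed correlation of Day 3 volume with less loss before Day 3 | p<0.05, Day 1-5 rule | p<0.05, Day 3-5 rule |
|---|---|---|
| 0 | 4% | 4% |
| 0.3 | 20% | 5% |
| 0.5 | 49% | 4% |

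This shows that the mechanism works. It does not give its size in this trial.

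**6. The mPVS denominator.** SAP 7.2 computes mPVS as (mPV - iPV)/iPV, with iPV = 39 mL/kg (men) times the lowest weight on Days 1 to 5. Take a man of 85 kg on Day 3 (assumed, and his lowest weight so far) with mPVS at +10%, the top of the normal range in 7.7.1. If he then loses 1.6 kg, iPV falls from 39 × 85 = 3,315 mL to 39 × 83.4 = 3,252.6 mL. His Day 3 mPVS becomes 1.10 × 3,315/3,252.6 - 1 = +12.1%, so he moves from normal to high because of weight lost after the measurement. This acts against the mechanism in step 5.

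**The case against.** **4.3.1 already supplies the windows.** It gives dose increases 24- and 48-hour windows from each index day, and the 24-48 hour phrase in 7.7.1 might govern the items before it. This stands for dose increases: a reader might infer that they are counted from Day 1, but 7.7.1 gives no start day and 4.3.1 points forward. For thiazide, the Day 1 wording could be meant only as a lower bound, so that existing treatment is not counted as added; the text is open to that. Neither reading rescues the weight component, whose Day 1-5 span is explicit.

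**The direction of bias is not established.** A reader might infer that the definition favours a positive result for the FAST measurement. The documents do not support that. With the SAP 7.2 denominator included, simulations with no true later link gave odds ratios for high Day 3 mPVS of roughly 0.5 to 2.1 under the Day 1-5 weight rule and 0.5 to 1.2 under a Day 3-5 rule. They assumed a mean loss of 0.6-1.0 kg/d (SD 0.6-0.8), correlation 0-0.5 between the two periods, 85 kg, PVS mean 5% and SD 8-15 points, and 1-4 PVS points per kg. Both ranges include 1. They also concern dichotomised mPVS and one component, whereas 7.7.1 names mPV and mTBV as the independent variables. This objection stands in full.

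**The stakes are small.** SAP 7.1 calls all analyses, p values included, descriptive. That limits the weight of the point but does not make the outcome definition correct.

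**Conclusion.** The point holds for the Day 3 model. The weight component is wrong as written, with 45% to 55% of its window before the measurement. Added thiazide has the same fault on its literal reading. Dose increases and symptom failure lack an anchor in 7.7.1, and 7.7.1 and 4.3.1 disagree on both windows and components. The misclassification in the two worked patients is arithmetic and needs no assumption beyond a count of days.

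The consequence is that the Day 3 model can show an association created by earlier events. Its size and direction depend on how closely Day 3 volume follows earlier diuresis and, for mPVS, on the lowest-weight denominator. No odds ratio should be quoted as the bias. It would also be too strong to say that a Day 3-5 weight window alone makes an mPVS analysis prospective, because Day 3 mPVS contains later weights.

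The Day 1 model looks forward in any case, although its weight window runs beyond 48 hours. One exploratory secondary analysis is affected; the primary endpoints are not. The SAP should be corrected before analysis.

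**What to change.** Reconcile SAP 7.7.1 with 4.3.1 by defining each component separately for each index day and counting only what follows that day's measurement:

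- **Weight:** change over Day 1-3 for the Day 1 model and Day 3-5 for the Day 3 model, at the SAP's own 0.5 kg/d.
- **Thiazide, dose increases, ultrafiltration/RRT:** within 24 and 48 hours after the measurement. Protocol Table 9 records doses from 06:00 to 06:00 the next day. Count the record that starts on the index day in the outcome window and compare it with the preceding 24-hour record. Starting only on the day after would miss an escalation ordered on Day 3 straight after the measurement.
- **PGA and dyspnea:** improvement measured from the index-day score.
- **Predictor:** use mPV and mTBV as 7.7.1 states, or note that Day 3 mPVS and mTBVS contain later weights.
- **Bookkeeping:** list thiazide and weight loss in 4.3.1 and record their addition in section 8. Keep the Day 1-5 weight rule, if wanted, as a descriptive variable.

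The cost is SAP wording only: Protocol Tables 1, 6 and 9 already provide weight, symptoms and diuretic doses on Days 1 to 5. There are two downsides. A two-day weight change is noisier than a four-day mean, and the index-day dose record may include some hours before the measurement.

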- To evaluate whether patients with low mPV or low mTBV (cutoffs potentially adjusted for some of the following variables age, gender, body height, body weight, optimal body weight (dry weight), hematocrit) on day 1 or on day 3 are at risk of developing low-output complications within the next 24-48 hours (e. g. subjectively reported dizziness/nausea, PGA, hypotension, need for iv-fluid therapy). Optimal logistic regression models will be selected by comparing the results of different variable selection models for the corresponding linear model (backward selection based on p-Values and Akaike Information Criterion, best subset selection, etc.).
- To evaluate whether patients with a high mPV or a high mTBV (cutoffs potentially adjusted for some of the following variables age, gender, body height, body weight, optimal body weight (dry weight), hematocrit) on day 1 and/or day 3 are at risk of being refractory to diuretic therapy (e. g. require dosage increases of furosemide/torsemide, require ultrafiltration/RRT within the next 24-48 hours, fail to improve subjectively in PGA and dyspnea scales). Optimal logistic regression models will be selected by comparing the results of different variable selection models for the corresponding linear model (backward selection based on p-Values and Akaike Information Criterion, best subset selection, etc.).
- To evaluate whether the time course of ePV and estimated TBV (eTBV) from day 1 to day 3 adequately reflects the time course of mPV and mTBV at these time points. Mean ePV and mPV and mean eTBV and mTBV will be compared for each time point separately (using paired t-tests) and by investigating the whole time curve (comparing the times when maximal and minimal volumes are reached and the areas under the curve)).
- To evaluate whether the change of mPV and mTBV from day 1 to day 3 is predictive of length of stay, dialysis/ultrafiltration requirement, or rehospitalization within 30 days, or mortality. Linear, logistic or Cox-regression models will be utilized as appropriate.
- To evaluate whether the time course of mGFR from day 1 to day 3 correlates temporally with or predicts the time course of eGFR within the next 24-48 hours.

eGFR and mGFR will be compared for each time point separately (using paired t-tests) and by investigating the whole time curve (comparing the times when maximal and minimal GFRs are reached and the areas under the curve).

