## 7.2 Derived Parameters

The following formulas will be used for determination of estimated and measured TBV, ideal TBV, estimated and measured total blood volume status (eTBVS and mTBVS), ePV, estimated PV change, ideal PV, estimated and measured plasma volume status (ePVS and mPVS), and eGFR on day 1 and day 3:

Nadler formula for eTBV (Sharma & Sharma, 2020):

- Men:  $eTBV [L] = (0.3669 \times \text{Height [m]}^3) + (0.03219 \times \text{Weight [kg]}) + 0.6041$
- Women:  $eTBV [L] = (0.3561 \times \text{Height [m]}^3) + (0.03308 \times \text{Weight [kg]}) + 0.1833$

mTBV will be calculated as follows:

- $mTBV [mL] = mPV [mL] / (1 - \text{hematocrit [\%]} / 100)$

Lemmens-Bernstein-Brodsky formula for ideal TBV (iTBV) (Lemmens, Bernstein, & Brodsky, 2006):

- $iTBV [mL/kg] = 70 / [\text{sqrt}(\text{body mass index}/22)]$  – the lowest body weight during the days 1 to 5 will be used for calculation of BMI
- $iTBV [mL] = iTBV [ml/kg] \times \text{weight [kg]}$  – the lowest body weight during the days 1 to 5 will be used for calculation

Estimated and measured total blood volume status:

- $eTBVS [\%] = \text{Percentage change from iTBV: } (eTBV - iTBV) / iTBV$
- $mTBVS [\%] = \text{Percentage change from iTBV: } (mTBV - iTBV) / iTBV$

Kaplan-Hakim Formula for ePV (Ling et al., 2015):

- Men:  $ePV [mL] = (1 - \text{hematocrit [\%]}) \times [1530 + (41 \times \text{weight [kg]})]$
- Women:  $ePV [mL] = (1 - \text{hematocrit [\%]}) \times [864 + (47.9 \times \text{weight [kg]})]$

Strauss formula for plasma volume change (Strauss, Davis, Rosenbaum, & Rossmeis, 1951):

- $PV\_2/PV\_1 \times 100 [\%] = \text{hemoglobin\_1 [g/dL]} / \text{hemoglobin\_2 [g/dL]} \times (1 - \text{hematocrit\_2 [\%]}) / (1 - \text{hematocrit\_1 [\%]}) \times 100$

Plasma volume change will also be calculated via the ratios of ePV by the Kaplan-Hakim-Formula

Harrison formula for ideal PV (iPV) (from Ling 2015):

- Men: iPV [mL] = 39 [mL/kg] × weight [kg] – the lowest body weight during the days 1 to 5 will be used for calculation
- Women: iPV [mL] = 40 [mL/kg] × weight [kg] – the lowest body weight during the days 1 to 5 will be used for calculation

Estimated and measured plasma volume status (ePVS and mPVS):

- ePVS [%] = Percentage change from iPV: (ePV - iPV)/iPV
- mPVS [%] = Percentage change from iPV: (mPV - iPV)/iPV

The eGFR will be calculated using CKD-EPI formula (Levey et al., 2009):

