To evaluate whether eGFR calculation by the CKD-EPI formula and sMDRD formula on days 1 and 3 provides an accurate estimate of measured GFR (mGFR; assessed by FAST methodology) in heart failure patients undergoing active fluid management, linear regression models with the measured value at a given day as dependent variable and the estimated version as independent variable will be generated. The models will be adjusted for mPV and mPVS. Further, Bland-Altman plots will be generated comparing the estimated and measured parameters separately for day 1 and day 3. The defined limits of agreements are  $\pm 6\text{ml/min}$ . Diagnostic accuracy including frequencies of values between 15% and 30% of the measured value will be determined as mentioned before.

To evaluate whether patients with a low mGFR/eGFR ratio on days 1 and 3 are at higher risk of developing AKI within the following 72 (day 1) and 48 (day 3) hours, logistic regression models with the AKI status as dependent variable and mGFR/eGFR ratio as independent variables will be generated. The models will be adjusted for mPVS, mTBVS. Three different versions of the mGFR/eGRF ratio will be evaluated: ratio  $< 1$ ; ratio  $<$  first quartile; ratio as continuous parameter.

To evaluate whether ranges of mPVS (low mPVS ( $< -10\%$ ), normal mPVS ( $-10$  to  $+10\%$ ), high mPVS ( $> +10\%$ )) and/or mTBVS (low mTBVS ( $< -10\%$ ), normal mTBVS ( $-10$  to  $+10\%$ ), high mTBVS ( $> +10\%$ )) on days 1 and 3 are associated with subjectively reported symptoms (current PGA  $> 15$ , current dyspnea  $> 15$ , current dizziness  $> 15$ , current nausea  $> 15$ ) determined using patient symptom assessment sheets within the following 24-48 hours, a logistic regression

---

model with occurrence of symptoms (PGA, dyspnea, dizziness, nausea) as dependent variable and the categorized measured value (mPVS, mTBVS) as independent variables will be generated. The models will be adjusted for mean arterial pressure.

To evaluate whether patients with low mPVS ( $< -10\%$ ) or low mTBVS ( $< -10\%$ ) on day 1 or on day 3 are at risk of developing low-output complications within the next 24-48 hours (subjectively reported dizziness  $> 15$ , nausea  $> 15$ , PGA  $< 25$ , hypotension (Systolic  $< 100$ , diastolic  $< 60$  mmHg), need for iv-fluid therapy), logistic regression models using mPVS and mTBVS as independent variables will be used.

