## 8 Changes from the protocol

In general, no variable selection will be done in the regression models due to limited sample size. Rather clinical expertise regarding the most important explanatory variables will be used to determine a fixed, hierarchical set of possible covariates.

The mPVS and mTBVS are used to determine patients with low, normal or high PV and TBV and thus, the status will be defined based on established estimation formulas for ideal PV and TBV incorporating weight and/or height.

The analysis of the time course of estimated and measured PV and TBV via t-tests was replaced by Bland-Altman-analyses since these analysis better reflects the underlying question of clinically equivalent measurements. Further, the curve characteristics (e.g. times when maximal and minimal volumes are reached and the areas under the curve) based on only few time points were deemed to be of minor meaningfulness.

Haemoglobin for estimating plasma volume changes by Strauss formula and cystatin C values to estimate Glomerular Filtration Rate were also recorded during the study and will also be utilized for the analysis in the respective estimation formulas.

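### SAP 7.7.1, refractory-to-diuretics analysis: the question concerns high volume status but the named model enters volume in mL, and once status is entered it shares Day 1-5 weights with the outcome

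*SAP*

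**What the plan says.** SAP 7.7.1 introduces the analysis with the words "To evaluate whether patients with a high mPVS", sets the cutoff for mPVS and mTBVS at above +10%, and closes by saying that "logistic regression models using mPV and mTBV as independent variables will be used". The low-output analysis just before it is built the same way, but there "logistic regression models using mPVS and mTBVS as independent variables will be used". SAP section 8 gives the general rule: "The mPVS and mTBVS are used to determine patients with low, normal or high PV and TBV".

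Status is defined in SAP 7.2 as the percentage deviation of the measured volume from an ideal volume. For both ideal volumes (iPV and iTBV), "the lowest body weight during the days 1 to 5 will be used for calculation".

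The refractory outcome in SAP 7.7.1 lists a diuretic dose increase, an added thiazide, ultrafiltration or RRT, no subjective improvement, and "fail of mean weight loss during the study period Day 1-Day 5 of at least 0,5 kg/d". The SAP does not say whether one component is enough. SAP 4.3.1 describes the outcome with a shorter window, ending "fail to improve subjectively in PGA and dyspnea scales) within 24 and 48 hours on day 1 and day 3".

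**The concern.** Two problems follow, and they belong to alternative readings of the model.

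- **Model as written (mL).** The +10% threshold in the question never enters the model. A large man can have a high volume in mL and a low status, so the fitted coefficient answers a different question.
- **Model with status entered.** Weights recorded after the Day 1 measurement help to define Day 1 status, and the same weights help to decide who is refractory. Greater weight loss raises status and makes the patient less likely to count as refractory. Part of any association would be arithmetic, in the direction opposite to the one the SAP wants to examine.

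At stake is how one hypothesis-generating result is read. The primary endpoints and the measured mPV and mTBV are not affected.

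**Working it through.** The plan gives no sample size, power or event figure for this analysis, so there is none to reproduce. The formulas come from SAP 7.2. Everything marked as assumed is not in the documents.

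**1. Is the mL wording mere shorthand?** The documents use the two kinds of variable as distinct. The length-of-stay analysis in SAP 7.7.1 fits changes in mPV and mTBV as a first model and changes in mPVS and mTBVS as a second. The eGFR models are adjusted for mPV and mPVS. The low-output analysis enters status.

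**2. mL against status (men).** iPV = 39 mL/kg × lowest Day 1-5 weight; mPVS = (mPV − iPV)/iPV.
- 3500 mL, 100 kg: 3500/3900 − 1 = −10.3% (low).
- 3300 mL, 75 kg: 3300/2925 − 1 = +12.8% (high).
- The same 3400 mL is +24.5% at 70 kg, +9.0% at 80 kg and −12.8% at 100 kg.

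With assumed weight SD 12-18 kg and mPV CV 15-25%, the squared correlation of mL with mPVS is 0.29-0.73.

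**3. The shared weights, one patient.** Take an 85 kg man who is 8% above ideal on his Day 1 weight: mPV = 39 × 85 × 1.08 = 3580 mL. If he loses 2 kg, the lowest weight is 83 kg, iPV = 39 × 83 = 3237 mL, and his Day 1 mPVS becomes 3580/3237 − 1 = +10.6%. The 2 kg moves him into the high group and also meets 0.5 kg/d × 4 intervals = 2.0 kg, so he is not refractory on that component. (Counting five days, the threshold would be 2.5 kg.)

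**4. Size of the pull when nothing is true.** Simulated under assumed inputs: Day 1 weight mean 88 kg, SD 18; status mean +5%; Day 1-5 loss mean/SD 2/2, 3/2, 3/3 and 4/3 kg; the weight component is a loss below 2 kg. The figures are odds ratios of high mPVS for being refractory.

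| Assumption | Weight component alone | Any one component counts, 30-50% meet another, independent one |
|---|---|---|
| mPV follows Day 1 weight, CV 20% | 0.64-0.76 | 0.76-0.87 |
| mPV follows Day 1 weight, CV 15-25% | about 0.55-0.80 | about 0.70-0.89 |
| mPV follows dry weight, CV 20% | 0.84-0.99 | 0.91-1.00 |

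The dry-weight row assumes dry weight mean 82 kg, SD 17, excess fluid mean 5 or 8 kg, and about half of the excess lost. For mTBVS (Day 1 weight, CV 20%) the pull is weaker, 0.80-0.87 for the weight component alone, because at fixed height iTBV grows with the square root of weight.

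**5. Against precision at N=50.** The standard error of the log odds ratio is about 0.57-0.66 in the composite settings at CV 20%. ln(0.76)/0.57 = −0.48 and ln(0.87)/0.60 = −0.23, so the pull is a quarter to a half of one standard error. Taking 0.70 with the same 0.57 gives −0.63. Under dry weight it is at most 0.15 at CV 20%.

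**6. Removing the weight component.** The null odds ratio returns to 0.99-1.00. If the other components are themselves linked to poor weight loss (assumed latent correlation 0.3), it is 0.87-0.92 (Day 1 weight) or 0.95-0.99 (dry weight).

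**7. Day 3 predictor.** A patient who loses 3 kg by Day 3 and nothing afterwards passes the Day 1-5 rule (3/4 = 0.75 kg/d) with no loss after the predictor. Counting loss only from Day 3 to Day 5 corrects the timing but moves the null odds ratio from 0.83-0.90 to 0.75-0.84, because the lowest weight still includes Days 4 and 5.

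**The case against.** The strongest reply is that the clause is a leftover from the protocol's wording about high mPV or mTBV, and that section 8 and the cutoffs in the same sentence already tell a statistician what is meant. That is probably how it arose. But the analysis names its predictors explicitly, and the SAP elsewhere fits volumes and status as separate models, so an analyst following the text would fit the wrong variable.

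It is also fair that the coupling is absent from the model as written, which contains no weight. Its size rests on whether mPV follows Day 1 or dry weight, which the documents cannot settle. All analyses, p values included, are declared descriptive (SAP 7.1). These points stand and limit the weight of the finding.

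Three stronger readings are tempting and should not be drawn.

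- **A clear gain in power from entering status.** A simulation whose outcomes are generated from continuous status favours continuous status by construction. For a true odds ratio of 2 per SD of mPVS at N=50, the > +10% category detects it in about 40-43% of runs and mL in 19-39%. In the most favourable setting for mL there is almost no gain. The reason to change is that the model should match the question.
- **An undisclosed change of outcome.** Weight loss is missing from the refractory lists in SAP 4.3.1 and in the protocol's secondary objectives ("require ultrafiltration/RRT within the next 24-48 hours, fail to improve subjectively in PGA and dyspnea scales"). Both lists are given as examples, and the protocol synopsis already names successful body weight reduction among the recorded outcomes. Its absence from section 8 is not a fault.
- **A timing error that a Day 3-5 count would cure.** The weight component has its own stated period, and the shorter count enlarges the coupling.

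**Conclusion.** The mismatch is real on the text and needs no assumption: the question is about status above +10%, the model is in mL, and the low-output analysis and section 8 both use status. Correcting the names alone would bring in the shared Day 1-5 weights, so the two matters should be handled together.

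The pull from the shared weights runs against the SAP's hypothesis. Its size is conditional on the assumed weight distribution, weight loss and mPV variability, on mPV following Day 1 weight, and, for the composite figures, on one component being sufficient. It is modest relative to precision at N=50 and smaller still under dry weight. The documents do not support a claim that it would reverse or dominate the result. For the Day 3 predictor, Day 1-5 weight loss partly precedes the predictor; this is a limitation to note.

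One secondary, descriptive analysis is affected. Severity: minor.

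**What to change.** In the refractory analysis of SAP 7.7.1:

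1. Replace mPV and mTBV by mPVS and mTBVS as independent variables, entered with the > +10% category and also as continuous values.
2. Report the refractory outcome with and without the weight-loss component, and read the version without it as free of the direct coupling.
3. For the Day 3 predictor, note that Day 1-5 weight loss partly precedes it and rely on the version without the weight component. Do not switch to a Day 3-5 count alone.
4. Optionally, repeat with iPV and iTBV based on the last stable body weight before admission, which is already recorded on Day 1 (protocol Table 6, SAP 4.1). Present this as a sensitivity analysis and not a cure: the null odds ratio is 1.00 if mPV follows dry weight, but still 0.70-0.84 for the weight component if it follows Day 1 weight.

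The cost is two variable names and one or two extra exploratory tables, with no new data. The version without weight loss gives up an objective sign of diuretic response and keeps some pull if the other components are linked to weight loss. The last stable weight may be missing or approximate.
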